2. OBJECTIVES

The objectives of this study are to:

1. Evaluate the therapeutic equivalence of the Test product, Tazarotene Cream 0.1% (Fougera Pharmaceuticals Inc.) to the Reference product, TAZORAC[®] (tazarotene) Cream 0.1% (Allergan, Inc.) in the treatment of acne vulgaris.
2. Demonstrate the superiority of the efficacy of the Test and Reference (active) products over that of the Placebo in the treatment of acne vulgaris.
3. Compare the safety of the Test, Reference and Placebo products in the treatment of acne vulgaris.

3. OVERALL STUDY DESIGN

This multi-center, double-blind, randomized, vehicle-controlled, parallel-group bioequivalence clinical study has been designed to evaluate the efficacy and safety of a generic tazarotene cream

[REDACTED]

STATISTICAL ANALYSIS PLAN

Tazarotene Cream 0.1%

Protocol / [REDACTED] 0454-01-01/[REDACTED]

0.1% (Fougera Pharmaceuticals Inc.) compared to the FDA Reference Listed Drug (RLD) TAZORAC[®] (tazarotene) Cream, 0.1% (Allergan) in subjects with a clinical diagnosis of acne vulgaris. Additionally, both the Test product and Reference (i.e., the RLD) product will be tested for superiority to a Placebo. Subjects with confirmed facial acne vulgaris will apply the investigational product (IP) once daily, in the evening, for 84 days \pm 4 days (12 weeks).

Before any study-specific procedures are performed, all subjects will read and sign the IRB-approved ICF. For a subject considered to be a minor in the state he/she is screened, the parent or legal guardian will be required to sign the ICF and the subject will sign an IRB-approved “assent to participate” form, as applicable.

Each site will develop an individualized recruitment plan to collectively enroll approximately 1110 eligible subjects, \geq 12 to \leq 40 years of age, with a clinical diagnosis of acne vulgaris and meeting the inclusion/exclusion criteria. Subjects will be randomized to one of the three IPs as follows:

- Test: Tazarotene Cream 0.1% (Fougera Pharmaceuticals Inc.)
- Reference: TAZORAC[®] (tazarotene) Cream, 0.1% (Allergan, Inc.)
- Placebo: Placebo (vehicle) Cream (Fougera Pharmaceuticals Inc.)

Subjects will attend the following scheduled clinic visits:

- Visit 1 - Screening/Baseline: Day -14 to 1
- Visit 2 - Interim Visit: Day 28 \pm 4 days
- Visit 3 - Interim Visit: Day 56 \pm 4 days
- Visit 4 - End of Study: Day 85 \pm 4 days

Subjects may attend unscheduled clinic visits:

- Visit 9999 – Unscheduled visit

At Visit 1, eligible subjects will be randomized to the Test, Reference or Placebo product in a 2:2:1 ratio using [REDACTED], which is an interactive response technology (IRT) system provided by the IRT provider. Study subjects will be provided with [REDACTED] of IP. At Visit 2 and/or Visit 3, subjects who continue to be eligible for continuation in the study can be dispensed another [REDACTED] of investigational product, as needed, based on the amount of IP remaining from the tube previously dispensed. Further, any empty tubes will be collect at these visits. At Visit 4, all tubes will be collected (used and unused). A subject may return for an Unscheduled Visit at any time, should they require a resupply of IP (i.e., tube lost; all IP used between visits). It is estimated that up to [REDACTED] will be needed to dose the subject for the treatment period. Additional tubes beyond the initial [REDACTED] will only be dispensed if the initial supply is lost and/or significantly damaged (i.e., becomes punctured) and warrants replacement.

[REDACTED]

STATISTICAL ANALYSIS PLAN

Tazarotene Cream 0.1%

Protocol / [REDACTED] 0454-01-01/[REDACTED]

The day that the subject administers their first dose of IP will be considered Day 1. [REDACTED]

[REDACTED] For all other subjects, the first dose (Day 1) of IP will be applied on the evening of Visit 1.

The subject will be instructed to apply a thin layer (2 mg/cm²) of the product once daily, in the evening, through the evening before Visit 4 (Day 85 ± 4). There will be no application of the product on the day of the End of Study visit.

Efficacy evaluations will be based on dermatological assessments in the clinic. The two co-primary statistical analyses of interest are (1) the percent change from Baseline to Week 12 in the inflammatory (papules/pustules) lesion counts and (2) the percent change from Baseline to Week 12 in the non-inflammatory (open and closed comedones) lesion counts. The secondary analysis is the proportion of subjects who are considered a Clinical Success at Week 12, as defined by an IGA score that is at least 2 grades less than the Baseline assessment. A Clinical Failure is defined as an IGA score that is the same, higher or one grade lower than the Baseline IGA at Week 12 (Appendix A).

STATISTICAL ANALYSIS PLAN

Tazarotene Cream 0.1%

Protocol / 0454-01-01/

Study Schematic

PROCEDURE	VISIT 1 (Day -14 to 1) Screening/ Baseline	VISIT 2 (Day 28 ± 4 Days) Interim Visit	VISIT 3 (Day 56 ± 4 Days) Interim Visit	VISIT 4 (Day 85 ± 4 Days)* End of Study/ Early Termination
Informed Consent/Assent	X [‡]			
Medical History/ Demographics	X [‡]			
Pregnancy Test [†]	X [‡]	X	X	X
Vital Signs	X [‡]			X
Lesion Counts	X [‡]	X	X	X
Investigator's Global Assessment	X [‡]	X	X	X
Application Site Reactions	X	X	X	X
Inclusion/Exclusion Criteria Review	X [‡]			
Concomitant Medication	X [‡]	X	X	X
Randomization	X			
Dispense IP	X	X**	X**	
Return of IP		X**	X**	X
Dispense Subject Diary /Supplies	X	X	X	
Collect/Review Subject Diary		X	X	X
Adverse Events		X	X	X
Discharge from Study				X

* Dosing regimen is once daily in the evening through the evening for 84 days (Day 1 to Day 84) before Visit 4 (Day 85 ± 4)

** If applicable, based on use of previously dispensed product.

† For females of childbearing potential

‡ Procedures performed as part of the screening assessment, before randomization

[REDACTED]

STATISTICAL ANALYSIS PLAN

Tazarotene Cream 0.1%

Protocol / [REDACTED] 0454-01-01/[REDACTED]

4. RANDOMIZATION AND BLINDING

The IP will be randomized, packaged and blinded by an [REDACTED]. The randomization code will be generated using a validated computer program.

[REDACTED] Each site will receive multiple, full blocks of IP in each delivery. The quantity received may vary.

Randomization will be pre-planned according to a computer-generated randomization scheme. The randomization code will be retained within [REDACTED] which is maintained by [REDACTED]. [REDACTED] will also retain the kit boxes numbers supplied to each site and the kit boxes numbers that have been selected for retention and are therefore unavailable for dispensing to subjects.

Upon confirmation of subject eligibility, the subject's information (i.e., subject's initials, date of birth, etc.) will be entered into [REDACTED], and the system will assign a [REDACTED] randomization number to the subject based upon [REDACTED]. [REDACTED] will then assign the subject a [REDACTED] kit box number in a blinded fashion at Visit 1. This kit box number will correspond to a specific treatment group within [REDACTED]; however the treatment group will be unknown to the Investigator, the CRO, the sponsor and the subject. The site will record the randomization number and the kit box number in the subject's source documentation and drug dispensing log. The [REDACTED] will then dispense [REDACTED] from the kit box. The [REDACTED] will record the tube number of the [REDACTED] dispensed to the subject in the subject's source documentation and drug dispensing log. At Visits 2, 3 and/or Unscheduled Visit, additional IP may be dispensed to the subject, as needed. The [REDACTED] will select an additional unused tube from the subject's previously assigned kit box, dispense it to the subject and record the tube number. [REDACTED]

[REDACTED] Each subject will maintain the same treatment assignment throughout the study.

5. SAMPLE SIZE

Sample size calculations were performed using [REDACTED]. For the primary endpoint analysis (percent change from Baseline at Week 12 (Study Day 85 ± 4 days) in inflammatory and non-inflammatory lesion counts), the sample size is estimated for therapeutic equivalence of the Test to the Reference product and superiority of each of the active treatments groups over Placebo. As no variability data were available for TAZORAC® Cream, 0.1%, the sample size estimations are based on data reported in the [REDACTED]

[REDACTED]

STATISTICAL ANALYSIS PLAN

Tazarotene Cream 0.1%

Protocol / [REDACTED] 0454-01-01/[REDACTED]

In the PP population, the mean percent reduction in inflammatory lesion count in the Reference treatment group at Week 12 is expected to be approximately [REDACTED], with a SD of [REDACTED] (coefficient of variation of [REDACTED]). The mean percent reduction in non-inflammatory lesion count in the Reference treatment group at Week 12 is expected to be approximately [REDACTED], with a SD of [REDACTED] (coefficient of variation of [REDACTED]). Based on these numbers, a sample size of [REDACTED] subjects per active treatment group in the PP population will provide approximately [REDACTED] power to demonstrate that the adjusted 90% confidence interval for the T/R ratio of least-squares treatment means for the primary endpoint is contained within the pre-defined equivalence limits [80%, 125%], if the true ratio is [REDACTED] and assuming [REDACTED] correlation between inflamed and non-inflamed lesion counts.

In the mITT population, the mean percent reduction in inflammatory and non-inflammatory lesion counts in the Placebo group is expected to be approximately [REDACTED] ([REDACTED], SD) and [REDACTED] ([REDACTED], SD), respectively. With a conversion rate of [REDACTED] from the mITT to the PP population, [REDACTED] subjects in each active group and [REDACTED] subjects in the Placebo group are required in the mITT population for the superiority analyses. This sample size will ensure sufficient power [REDACTED] to show a difference at $p < 0.05$ (two-sided) between each active treatment group and the Placebo group for each endpoint, assuming 0% correlation between the inflamed and non-inflamed lesion counts and [REDACTED] correlation between the two superiority tests for each endpoint. Under the above assumptions, the overall study power to demonstrate therapeutic equivalence and superiority for the primary endpoint is estimated to be at least [REDACTED]. To allow for approximately [REDACTED] subjects who may drop out from the study or are otherwise non-evaluable, up to 1110 subjects will be enrolled (444 in each active group and 222 in the Placebo group).

6. ANALYSIS POPULATION

Per-Protocol Population

The PP population will include subjects that comply with the protocol as follows:

- All randomized subjects who meet all inclusion and exclusion criteria.
- Make the final study visit (Visit 4) within the protocol window of Day 85 ± 4 days with no PDs that would affect the integrity of the data.
- Comply with study restrictions including concomitant medications.
- Apply the IP appropriately and are within [REDACTED] compliant with dosing during the 12 weeks (Day 85 ± 4) of treatment.
- Do not miss the scheduled applications for more than [REDACTED]

[REDACTED]

STATISTICAL ANALYSIS PLAN

Tazarotene Cream 0.1%

Protocol / [REDACTED] 0454-01-01/[REDACTED]

[REDACTED]

[REDACTED]

Modified Intent-to-Treat Population (mITT)

The mITT population will include all subjects in the PP population plus all randomized subjects who meet all inclusion/exclusion criteria, apply at least one dose of assigned product, and return for at least one post-Baseline evaluation.

[REDACTED]

Safety Population

All subjects who are randomized and received IP will be included in the analysis of safety.

7. STUDY EFFICACY VARIABLES

Primary Efficacy Endpoints

The two co-primary efficacy endpoints are (1) the percent change from Baseline to Week 12 in the inflammatory (papules/pustules) lesion counts and (2) the percent change from Baseline to Week 12 in the non-inflammatory (open and closed comedones) lesion counts.

Secondary Efficacy Endpoint

The secondary efficacy endpoint is the proportion of subjects who are considered a Clinical Success at Week 12, as defined by an IGA score that is at least 2 grades less than the Baseline assessment. That is, at Week 12, subjects with an IGA score of 4 at Baseline must achieve a score of 0, 1 or 2, subjects with an IGA score of 3 at Baseline must achieve a score of 0 or 1, and subjects with an IGA score of 2 at Baseline must achieve a score of 0 to be considered a Clinical Success.

A Clinical Failure is defined as an IGA score at Week 12 that is the same, higher or one grade lower than the Baseline IGA. Subjects who are discontinued due to lack of treatment effect or worsening condition will be considered Clinical Failures.

STATISTICAL ANALYSIS PLAN

Tazarotene Cream 0.1%

Protocol / 0454-01-01/

8. STATISTICAL ANALYSIS METHODS

If not otherwise specified, statistical significance is defined as $p < 0.05$ and is two-tailed. Data will be summarized with respect to demographic and baseline characteristics, efficacy variables and safety variables.

For categorical variables, the number and percent of each category within a parameter will be calculated for non-missing data. For continuous variables with non-missing values, statistics will include number of observations, mean, standard deviation, median, minimum and maximum values.

All statistical analyses will be conducted using SAS[®], Version 9.4 or higher. Datasets will be prepared using headings from Clinical Data Interchange Consortium (CDISC) Study Data Tabulation Model (SDTM) implementation for human clinical trials and ADaM (Analysis Dataset Model).

8.1 Baseline Characteristics

8.1.1 Demographics Comparability of Treatment Groups

Baseline characteristics will be evaluated separately for the PP, mITT and Safety populations.

Demographic information collected at baseline includes the following:

- Age (years)
- Sex (Male/Female)
- Ethnicity (Hispanic/non Hispanic)
- Race (White, Black/African American, Native Hawaiian or Other Pacific Islander, Asian, American Indian or Alaska Native, Other)
- Baseline number of inflammatory lesions (i.e., papules and pustules)
- Baseline number of non-inflammatory lesions (i.e., open and closed comedones)
- Baseline number of nodulocystic lesions (i.e., nodules and cysts)
- Baseline IGA score

Summary tables by treatment group will be presented. Continuous variables will be summarized using descriptive statistics (number of observations, median, minimum, maximum, mean and standard deviation). Categorical variables will be summarized using frequencies and percentage. Baseline treatment comparisons will be presented using Chi-Square test for the categorical variables, and Analysis of Variance (ANOVA) for the continuous variables.

All data will be listed by treatment and patient.

[REDACTED]

STATISTICAL ANALYSIS PLAN

Tazarotene Cream 0.1%

Protocol / [REDACTED] 0454-01-01/[REDACTED]

8.1.2 Medical History

At Visit 1 subjects will be questioned about personal medical history including acne history. The medical history will include a complete review of all current diseases and their respective durations and treatments.

Medical history data will be listed by treatment and patient.

8.1.3 Concomitant Medications

At Visit 1, subjects will be questioned about current and prior concomitant medication use over the previous 6 months. At Visit 2, Visit 3 and Visit 4 subjects will be questioned about ongoing or new concomitant medication use.

All prior and concomitant medications taken since screening until the end of the study will be listed by treatment and patient.

8.1.4 Pregnancy Test

All females of childbearing potential will have a urine pregnancy test performed at each Scheduled visit. All females of childbearing potential will have a urine pregnancy test performed at Visit 1 (Baseline), Visit 2, Visit 3, and Visit 4 (or early termination).

Pregnancy test results will be listed by treatment and patient.

8.2 Efficacy Analyses

8.2.1 Primary Efficacy Analysis

Therapeutic Bioequivalence Analysis

The primary measure of therapeutic equivalence will be evaluated using the PP population, with results in the mITT population being supportive.

The following Statistical Analysis Method is recommended by OGD for equivalence testing for a continuous variable:

The compound hypothesis to be tested is:

$$H_0: \mu_T/\mu_R < \theta_1 \text{ or } \mu_T/\mu_R > \theta_2 \quad \text{versus}$$

STATISTICAL ANALYSIS PLAN

Tazarotene Cream 0.1%

Protocol / 0454-01-01/

$$H_A: \theta_1 \leq \mu_T / \mu_R \leq \theta_2$$

where μ_T = mean percent change from baseline of test treatment, and
 μ_R = mean percent change from baseline of reference treatment

Under the assumptions of normally distributed data, the adjusted 90% confidence interval will be calculated for the Test/Reference ratio of the mean percent change from Baseline in inflammatory and non-inflammatory lesion counts using an iterative procedure similar to Fieller's method. ANOVA with treatment and site as fixed effects in the model will be conducted on the mean percent change from Baseline to Week 12 in the inflammatory (papules/pustules) lesion counts and non-inflammatory (open and closed comedones) lesion counts. If the adjusted 90% confidence intervals for the least-squares mean Test/Reference ratios are within 80-125% for both co-primary endpoints, then therapeutic equivalence of the Test to Reference product will be considered to have been demonstrated.

To declare therapeutic equivalence of the Test product to the Reference product, therapeutic equivalence must be demonstrated for only the primary endpoints in the PP population.

Superiority to Placebo Analysis

The primary measure of superiority will be evaluated using the mITT population, using LOCF for missing efficacy values. The results in the PP population will be considered supportive.

The superiority of the Test and Reference products over Placebo is concluded if these treatments' mean percent changes from Baseline in inflamed and non-inflamed lesion counts at Week 12 are statistically superior to that of the Placebo at the 5% significance level ($p < 0.05$, two-sided). The superiority of Test and Reference treatments over the Placebo will be evaluated in the same ANOVA model for Test vs. Placebo and Reference vs. Placebo.

To declare superiority of the Test and Reference products over Placebo, their superiority must be demonstrated for only the primary endpoint in the mITT population.

8.2.2 Secondary Efficacy Analyses

The PP population will be used for analysis of therapeutic equivalence and the mITT population will be used for analyses of superiority.

Therapeutic Bioequivalence Analysis

[REDACTED]

STATISTICAL ANALYSIS PLAN

Tazarotene Cream 0.1%

Protocol / [REDACTED] 0454-01-01/[REDACTED]

Based on the usual method used in OGD for binary outcomes, the 90% confidence interval for the difference in success proportions between test and reference treatment should be contained within [-0.20, +0.20] in order to establish equivalence.

The compound hypothesis to be tested is:

$$H_0: P_T - P_R < -.20 \text{ or } P_T - P_R > .20 \quad \text{versus}$$

$$H_A: -.20 \leq P_T - P_R \leq .20$$

where P_T = success rate of test treatment
 P_R = success rate of reference treatment.

Let

n_T = sample size of test treatment group
 cn_T = number of subjects considered as clinical success in test treatment group
 n_R = sample size of reference treatment group
 cn_R = number of subjects considered as clinical success in reference treatment group
 $\hat{P}_T = cn_T/n_T$ $\hat{P}_R = cn_R/n_R$, and

$$se = (\hat{P}_T(1 - \hat{P}_T)/n_T + (\hat{P}_R(1 - \hat{P}_R)/n_R)^{1/2}$$

The 90% confidence interval for the difference in proportions between test and reference will be calculated as follows, using Yates' correction:

$$L = (\hat{P}_T - \hat{P}_R) - 1.645 se - (1/n_T + 1/n_R)/2$$

$$U = (\hat{P}_T - \hat{P}_R) + 1.645 se + (1/n_T + 1/n_R)/2$$

For the proportion of Clinical Success, if the 90% confidence interval (with Yates' Correction factor) of the difference between the proportion of subjects considered a Clinical Success in the Test and the Reference product groups at Week 12 is contained within -20% to +20%, then therapeutic equivalence of the Test to Reference product will be considered supported for the secondary endpoint.

Superiority to Placebo Analysis

The analyses for superiority will be conducted using the mITT population and LOCF.

For the determination of superiority, the proportion of subjects considered a Clinical Success at Week 12 in the Test and Reference product groups will each be compared to the proportion of

[REDACTED]

STATISTICAL ANALYSIS PLAN

Tazarotene Cream 0.1%

Protocol / [REDACTED] 0454-01-01 / [REDACTED]

subjects considered as Clinical Success in the Placebo group.

If the proportion of subjects showing Clinical Success in the Test and Reference groups is statistically significantly greater ($p < 0.05$; using Cochran-Mantel-Haenszel exact test stratified by clinical site)) than the Clinical Success seen in the Placebo group then superiority will be concluded.

A summary table with frequency and percentage of the proportion of Clinical Success by treatment group will be presented.

8.2.3 Treatment-by-Site Interaction and Pooling of Clinical Sites

As this is a multiple-site study, the interaction of treatment-by-site may be evaluated in the ANOVA model for evaluations involving the primary efficacy endpoint. [REDACTED]

[REDACTED] If no treatment-by-site interaction is identified with the primary endpoint then no adjustment will be made to any efficacy analysis and treatment-by site interaction will not be included as a term in the statistical models for evaluating therapeutic equivalence and superiority.

8.3 Safety Analysis

All safety analyses will be based on the Safety Population.

8.3.1 Adverse Events

All the adverse events (AEs) reported throughout the study will be coded and classified according to the MedDRA (Medical Dictionary for Regulatory Activities) coding dictionary (Version 18.1 or higher). Each adverse event is to be evaluated for date of start and end, seriousness, severity, relationship to the IP, action taken and outcome.

In each of the following categories, the total number and percentage of subjects with 1) at least one AE, 2) discontinued study drug due to AEs, 3) AE severity and AEs related to the IP, 4) serious AEs and death will be summarized separately by treatment groups.

A summary table of the number and percent of subjects with AEs by system organ class, preferred term, and treatment group will be presented. Each patient will be counted only once within each preferred term.

[REDACTED]

STATISTICAL ANALYSIS PLAN

Tazarotene Cream 0.1%

Protocol / [REDACTED] 0454-01-01/[REDACTED]

A frequency summary table of the number of AEs by system organ class, preferred term, severity, and treatment group will be presented. Severity will be classified as “Mild”, “Moderate”, or “Severe”.

Similarly, a frequency summary table of the number of AEs by system organ class, preferred term, and relationship to the IP, and treatment group will be presented. Relationship to a study drug will be classified as “Suspected” or “Not Suspected”.

Should sufficient data exist, adverse event frequencies will be compared between treatments using Fisher’s exact test.

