10.6.16 Health Status/AEs

At Visits 2, 3 and 4 subjects will be questioned regarding any changes in their medical status since their previous visit. Any significant health changes observed after signing of the ICF will be reported as AEs, as deemed appropriate by the Investigator.

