10.7.4 AE Documentation

Any AE (non-serious and serious) occurring after the subject has provided study-specific informed consent, and until the last study visit of the subject, has to be recorded on the AE pages of the eCRF.

The occurrence of AEs should be sought by non-directive questioning of the subject at each visit during the study. AEs also may be identified when they are volunteered by the subject during or between visits or during physical examination, laboratory test or other assessments. All AEs should be given appropriate medical care. Treatment may include one or more of the following: no action taken (i.e., further observation only); IP dosage adjusted/temporarily interrupted; IP permanently discontinued due to this AE; concomitant medication given; non-drug therapy given, subject hospitalized / subject's hospitalization prolonged. The treatment of the AE should be documented in the eCRF. In addition, the action taken with the IP should be documented, and should be assigned to one of the following categories: not changed, withdrawn, reduced, increased, interrupted, unknown and not applicable. Concomitant medication, other treatments or changes in the administration of the IP should be specified and documented.

Medical conditions/diseases present before starting IP are only considered AEs if they worsen after enrollment. Abnormal laboratory values or test results constitute AEs only if they induce clinical signs or symptoms, are considered clinically significant or require therapy.

Once an AE is identified, the Investigator should follow-up as specified below. Each time, the outcome should be documented and assigned to one of the following categories: not recovered/unchanged, condition deteriorating, recovered/resolved, improving/recovering, recovered/resolved with sequelae, fatal or unknown. The assessment of an AE should be made at each planned visit (or more frequently, if necessary). The Investigator should document in the eCRF any changes in seriousness, severity, the suspected relationship with the IP, the interventions required to treat it, and the outcome.

AEs occurring between informed consent and first dosing

Any AE occurring between study-specific informed consent and first dosing will be documented as "screening event", with an IP causality assessment "IP not yet administered".

CONFIDENTIAL PROTOCOL

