Test	xxx	xxx	xx.x%		
Reference	xxx	xxx	xx.x%	xx.x%	xx.x – xx.x

Superiority: modified Intent-to-Treat Population

Treatment Group	Number of Subjects (N)	Number of Treatment Successes (n)	Proportion of Treatment Successes (%)	P-value
Placebo	xxx	xxx	xx.x%	
Test	xxx	xxx	xx.x%	x.xxxx
Reference	xxx	xxx	xx.x%	x.xxxx

The 90% confidence interval for the difference in proportions between test and reference was calculated using Yates' correction.

Superiority of Active treatments over Placebo were tested using a two-sided Cochran-Mantel-Haenszel (CMH) exact test, stratified by clinical site, at the 5% significance level using last observation carried forward (LOCF).

Test: Tazarotene Cream 0.1% (Fougera Pharmaceuticals Inc.)
Reference: TAZORAC® (tazarotene) Cream, 0.1% (Allergan, Inc.)
Placebo: Placebo (vehicle) Cream (Fougera Pharmaceuticals Inc.)

**T16.1.9.12 Overall Summary of Adverse Events
(Safety Population)**

Description	Test N (%)	Reference N (%)	Placebo N (%)	Total N (%)
Subjects Randomized	xxx	xxx	xxx	xxx
Subjects with at least one AE	xx (xx.x%)	xx (xx.x%)	xx (xx.x%)	xx (xx.x%)
Discontinued study drug due to above AE	xx (xx.x%)	xx (xx.x%)	xx (xx.x%)	xx (xx.x%)
AEs reported	xxx	xxx	xxx	xxx
Mild	xx (xx.x%)	xx (xx.x%)	xx (xx.x%)	xx (xx.x%)
Moderate	xx (xx.x%)	xx (xx.x%)	xx (xx.x%)	xx (xx.x%)
Severe	xx (xx.x%)	xx (xx.x%)	xx (xx.x%)	xx (xx.x%)
Not Suspected	xx (xx.x%)	xx (xx.x%)	xx (xx.x%)	xx (xx.x%)
Suspected	xx (xx.x%)	xx (xx.x%)	xx (xx.x%)	xx (xx.x%)
Death	xx (xx.x%)	xx (xx.x%)	xx (xx.x%)	xx (xx.x%)
Serious AE	xx (xx.x%)	xx (xx.x%)	xx (xx.x%)	xx (xx.x%)

Test: Tazarotene Cream 0.1% (Fougera Pharmaceuticals Inc.)
Reference: TAZORAC® (tazarotene) Cream, 0.1% (Allergan, Inc.)
Placebo: Placebo (vehicle) Cream (Fougera Pharmaceuticals Inc.)

**T16.1.9.13 Summary of Frequency of All Adverse Events by Body System
(Safety Population)**

Body System	MedDRA Term	Test (N = xxx)		Reference (N = xxx)		Placebo (N = xxx)		Fisher's P-value
		Events	Subjects	Events	Subjects	Events	Subjects	
Patient with at least one AE	Total	Xx	xx (xx.x%)	xx	xx (xx.x%)	xx	xx (xx.x%)	x.xxxx
Ear and labyrinth disorders	Ear pain	Xx	xx (xx.x%)	xx	xx (xx.x%)	xx	xx (xx.x%)	x.xxxx
	etc.							
	etc.							

Comparison of treatment groups is with respect to the number of subjects with at least one occurrence of the AE.

Test: Tazarotene Cream 0.1% (Fougera Pharmaceuticals Inc.)
Reference: TAZORAC® (tazarotene) Cream, 0.1% (Allergan, Inc.)

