Placebo: Placebo (vehicle) Cream (Fougera Pharmaceuticals Inc.)

**T16.1.9.14 Summary of Frequency for AEs Occurring in at Least 5% of Subjects by Body System
(Safety Population)**

**T16.1.9.15 Summary of Frequency of All Adverse Events by Severity
(Safety Population)**

Body System	MedDRA Term	Test # Events (N=xx)			Reference # Events (N=xx)			Placebo # Events (N=xx)		
		Mild	Moderate	Severe	Mild	Moderate	Severe	Mild	Moderate	Severe
Total AEs	Total AEs	xx(xx.x%)	xx(xx.x%)	xx (xx.x%)	xx(xx.x%)	xx(xx.x%)	xx (xx.x%)	xx (xx.x%)	xx (xx.x%)	xx (xx.x%)
Ear and labyrinth disorders	Ear pain	xx(xx.x%)	xx(xx.x%)	xx (xx.x%)	xx(xx.x%)	xx(xx.x%)	xx (xx.x%)	xx (xx.x%)	xx (xx.x%)	xx (xx.x%)
	Hypoacusis	xx(xx.x%)	xx(xx.x%)	xx (xx.x%)	xx(xx.x%)	xx(xx.x%)	xx (xx.x%)	xx (xx.x%)	xx (xx.x%)	xx (xx.x%)

etc.

N = Total number of events in each treatment group; Percentage is based on total number of events.

Test: Tazarotene Cream 0.1% (Fougera Pharmaceuticals Inc.)

Reference: TAZORAC® (tazarotene) Cream, 0.1% (Allergan, Inc.)

Placebo: Placebo (vehicle) Cream (Fougera Pharmaceuticals Inc.)

**T16.1.9.16 Summary of Frequency of All Adverse Events by Relationship
(Safety Population)**

Body System	MedDRA Term	Test # Events (N=xx)		Reference # Events (N=xx)		Placebo # Events (N=xx)	
		Suspected	Not Suspected	Suspected	Not Suspected	Suspected	Not Suspected
Total AEs	Total AEs	xx (xx.x%)	xx (xx.x%)	xx (xx.x%)	xx (xx.x%)	xx (xx.x%)	xx (xx.x%)
Ear and labyrinth disorders	Ear pain	xx (xx.x%)	xx (xx.x%)	xx (xx.x%)	xx (xx.x%)	xx (xx.x%)	xx (xx.x%)
	Hypoacusis	xx (xx.x%)	xx (xx.x%)	xx (xx.x%)	xx (xx.x%)	xx (xx.x%)	xx (xx.x%)
	etc.						
etc.							

N = Total number of events in each treatment group; Percentage is based on total number of events.

Test: Tazarotene Cream 0.1% (Fougera Pharmaceuticals Inc.)

Reference: TAZORAC® (tazarotene) Cream, 0.1% (Allergan, Inc.)

Placebo: Placebo (vehicle) Cream (Fougera Pharmaceuticals Inc.)

**T16.1.9.17 Summary of Frequency of Serious Adverse Events
(Safety Population)**

Body System	MedDRA Term	Test # Events	Reference # Events	Placebo # Events
Injury, poisoning and procedural complications	Alcohol poisoning	xx	xx	xx

Test: Tazarotene Cream 0.1% (Fougera Pharmaceuticals Inc.)
Reference: TAZORAC® (tazarotene) Cream, 0.1% (Allergan, Inc.)
Placebo: Placebo (vehicle) Cream (Fougera Pharmaceuticals Inc.)

Path: L:\Studies_Sas_Codes\Clinical Trial\ [REDACTED] SAS\OUT

Created on: ddmmmyy hh:mm

Page 1 of N

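### The SAP's adverse event tables have no first-dose cut-off, so pre-dose screening events are counted under treatment arms, and two tables have no place for their causality value

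*SAP*

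**What the plan says.** **Collection (Protocol).** Section 10.7.4 has AEs recorded on the eCRF from consent to the last visit. It sets the earliest ones apart: "Any AE occurring between study-specific informed consent and first dosing will be documented as" a screening event, with causality "IP not yet administered". Section 10.6.16 adds that "Any significant health changes observed after signing of the ICF will be reported as AEs"; the same sentence leaves the decision to the Investigator's judgement.

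**Tabulation (SAP).** Section 8.3.1 takes all AEs reported throughout the study and promises that "A summary table of the number and percent of subjects with AEs by system organ class, preferred term, and treatment group will be presented". On causality it says "Relationship to a study drug will be classified as" Suspected or Not Suspected. It mentions neither first dose nor screening events.

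**Shells (SAP section 9).** T16.1.9.12, "Overall Summary of Adverse Events", has rows for Suspected and Not Suspected only. T16.1.9.13, "Summary of Frequency of All Adverse Events by Body System", carries a Fisher p-value on subjects with at least one occurrence. T16.1.9.16 has two relationship columns per arm, with the footnote "N = Total number of events in each treatment group; Percentage is based on total number of events". None of T16.1.9.12 to T16.1.9.17 restricts onset.

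**Pointing the other way.** Protocol 10.3.4 (withdrawal of subjects) refers to tabulating AEs after dosing up to withdrawal. The AE definition in Protocol 10.7.1 speaks of a subject who has been given a product.

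**The concern.** Objective 3 compares the safety of the three products. An event before the first application cannot have been caused by any of them, yet on the SAP's wording it is shown under the arm to which the subject was randomised and enters the between-arm test.

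The design builds in some pre-dose time. Subjects are randomised and given product at Visit 1, but females of childbearing potential must start dosing during menses (Protocol 10.4.1), and those who wait may do so for up to 14 days after the Visit 1 pregnancy test (10.6.4).

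The causality value is a second difficulty. In T16.1.9.12 and T16.1.9.16 a screening event must either be recoded to a category that the investigator did not choose, or stay in the total with no category. Protocol 10.7.3 has the sponsor treat missing causality as suspected, so a screening event misread as missing could be reported as suspected before any product was applied.

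**Working it through.** The plan gives no figure on this point to reproduce. The check is textual, followed by the size of the pre-dose window.

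**Does any visible rule remove pre-dose events?**
- SAP section 6, Safety Population: selects randomised subjects who received product. It removes undosed subjects, not the pre-dose events of dosed ones.
- Protocol 11.9: summarises AEs by treatment group with no onset condition.
- Protocol 10.3.4: speaks of events after dosing, but within the withdrawal section and about safety monitoring. SAP 8.3.1 does not carry it over.
- Protocol 10.7.1: the definition points to events after administration, but 10.7.4 still calls the earlier ones AEs and puts them on the AE pages.

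So the visible texts conflict, and nothing in the SAP settles the conflict.

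**Which tables lack the causality value?** Only T16.1.9.12 and T16.1.9.16. The shells for T16.1.9.13, .15 and .17 have no causality split, and the title of .14 indicates none.

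**Pre-dose share of observed days.** Inputs: longest wait 14 days (Protocol 10.6.4); dosing 84 ± 4 days (10.4.1). Share = 14 / (14 + dosing days).
- 80 days: 14/94 = 14.9%
- 84 days: 14/98 = 14.3%
- 88 days: 14/102 = 13.7%
- A subject who stops after, say, 28 dosing days: 14/42 = 33.3%
- A subject who doses on the evening of Visit 1: close to 0

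**Illustration on assumed values.** The documents give no AE rates and no share of subjects who wait. Assume that a share f waits w days, that the background event rate is constant, that the products cause no events and that reporting is complete. The pre-dose share of an arm's events is s = fw/(fw + 84). If screening events stay uncategorised, the two shares in T16.1.9.16 sum to 100(1 − s). For the between-arm effect, assume a 20% background AE incidence over 84 days and a true active–placebo difference of 10 points. Then q = 1 − 0.8^(w/84), and the tabulated difference is 10(1 − fq).

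| f | w (days) | s | Sum of shares | q | Difference (points) |
|---|---|---|---|---|---|
| 0.25 | 7 | 1.75/85.75 = 2.0% | 98.0% | 0.0184 | 9.95 |
| 0.50 | 7 | 3.5/87.5 = 4.0% | 96.0% | 0.0184 | 9.91 |
| 0.50 | 14 | 7/91 = 7.7% | 92.3% | 0.0365 | 9.82 |

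The value of s is an upper figure for its f and w if the product also causes events or pre-dose events are under-reported.

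**Second illustration.** Assume post-dose incidences of 30% (active) and 15% (placebo), and add an equal pre-dose incidence b to each arm: incidence = 1 − (1 − p)(1 − b). For b = 1%, 3% and 5% the difference falls from 15 to 14.85, 14.55 and 14.25 points, and the ratio from 2.00 to 1.94, 1.83 and 1.74. The pull is always towards similarity. In the table above the whole-arm pre-dose incidence fq is at most 0.5 × 0.0365 = 1.8%, so 5% is an extreme case.

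**The case against.** The strongest reply is that the Protocol already points to a post-dose count. Its AE definition presupposes administration. Section 10.3.4 is the one sentence that links AE tabulation to dosing, and its subject is all randomised subjects. Section 10.7.4 also says that conditions present before starting product count as AEs only if they worsen. This stands in part: the intent may well be post-dose tabulation. But that last sentence counts worsening from enrolment, not from first dose, and the SAP's instruction is to take all reported events. The result is a conflict, not a settled rule.

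Second, few such events may exist. Reporting under 10.6.16 is at the Investigator's discretion, and the schedule has AE rows only at Visits 2 to 4. The discretion stands and limits the numbers. The schedule does not exclude the events, since Visit 2 asks about changes since Visit 1.

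Third, SAP section 9 says that the shells may be adapted. A category or footnote can indeed be added later. Which events are counted is an analysis rule and is better fixed before unblinding.

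Fourth, some text is redacted, including first-dose timing, a Protocol subsection between 10.7.7 and 10.7.9, and an item after SAP Appendix B. None is known to hold an AE rule, but the absence is established for the visible text only.

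**Conclusion.** The point holds as a minor improvement. On the visible text, the SAP's by-arm AE tables and Fisher comparison include events before first dosing in subjects who are later dosed. That does not fit Protocol 10.7.4 or 10.3.4, and two tables cannot show the prescribed causality value.

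The size is small. The range of 13.7% to 14.9% of observed days applies to a completer who waits the full 14 days; it is not a ceiling, because an early terminator can exceed it. All effects on event shares and differences rest on assumed waiting shares and event rates.

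Two stronger readings are not supported. A reader might infer that the safety comparison is biased in favour of one product. Pre-dose events arise under blinded assignment before any product is applied, so they are balanced in expectation and only dilute a difference slightly; no equivalence, superiority or safety decision rule depends on them. A reader might also infer that the SAP breaches a clear protocol rule. The Protocol's post-dose wording is indirect, and its own statistical section states no cut-off.

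**What to change.** In SAP 8.3.1:
- Restrict T16.1.9.12 to T16.1.9.17 to AEs that start or worsen after first dosing, using first-dose date, AE start date and, where the eCRF captures it, the screening event label. An event that worsens after first dosing counts from the date of worsening.
- State a rule for onset on the day of first dose and for partial dates. For example, count the event as after first dosing unless the label or the known part of the date shows earlier onset.
- List screening events separately with causality "IP not yet administered". Do not map that value to Suspected or Not Suspected, and do not treat it as missing causality.

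The cost is SAP wording, one analysis flag and one extra listing. First-dose date and AE start date already appear in listings L16.2.5.2 and L16.2.7.1. Whether the screening event label, and separate severity and causality after worsening, are analysable fields should be checked against the eCRF, which is not among the documents.
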